**Collaborative Care is a healthcare model capable of providing specialty care to far more patients than can be achieved through traditional one-on-one treatment models.** Collaborative Care has proven effective in delivering treatments for managing depression and pain in primary care settings [12-15]. A few recent studies have also demonstrated efficacy in treating addiction and opioid dependence using a collaborative care approach [16, 17]. Several different pain interventions have been effective in these collaborative care trials, including medication optimization, cognitive behavioral therapy, and several different structured self-management programs. Recently, pain researchers have found positive psychology-based interventions to be effective, well-received, and easy to deliver [18-20], making this intervention well-suited to pair with collaborative care. In the proposed clinical trial, we will assess the feasibility of utilizing collaborative care to facilitate opioid tapering in patients with chronic pain using a positive psychology intervention.

**Primary Aim:** Determine the potential effectiveness of delivering Collaborative Care for reducing opioids in patients with chronic pain.

**Hypothesis:** Collaborative Care will be effective (30% reduction in mean morphine equivalent dose/day [MMED]) in reducing opioids while maintaining pain control (< 1 point increase in 0 to 10 pain rating scale).

**Secondary Aim:** Assess adherence to tapering and satisfaction of patients with this Collaborative Care approach.

**Hypothesis:** Patients will be satisfied with (mean score  $\geq 3$  on 0 to 5 satisfaction scale) and adhere to ( $\geq 70\%$  retention) the 12-week opioid tapering program.

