**Table 1. Previous Work by Team Relevant to CCODAP Trial**

Trial	[name] Role	N	Mo.	Symptoms Targeted	Patient Sample	Tele-care	Intervention	Benefits
AIM[25]	Co-PI	176	9	Depression	Neurology (stroke)	Partly	Medications	Intervention > Usual care
SCAMP[26, 27]	PI	250	12	Pain Depression	Primary care	Partly	Medications & Self-management	Intervention > Usual care
INCPAD[13, 28]	PI	405	12	Pain Depression	Cancer (all types)	Fully	Medications	Intervention > Usual care
SCOPE[14, 29]	PI	250	12	Pain	Primary care	Fully	Medications	Intervention > Usual care
CAMMPS[15, 30]	PI	300	12	Pain, Anxiety, Depression	Primary care	Fully	Medications & Self-management	NCM + ASM > ASM alone†
COPE[31, 32]	Co-Invest	495	6	Function Pain	Cancer (advanced)	Partly	Physical therapy & Pain management	Intervention > Monitoring only
SPACE[8, 33]	Co-Invest	240	12	Pain	Primary care	Partly	Medications	Non-opioids = Opioids
ESCAPE[34]	Co-Invest	241	9	Pain	Primary care	Partly	Medications + CBT	Intervention > Usual care

† NCM = nurse care management, ASM = automated symptom management

**Study Design.** Forty patients with non-cancer chronic pain on long-term oral opioid therapy will be recruited into this pilot trial. Patients will be randomized to receive either the treatment intervention (n = 20) or usual care (n = 20). Assignment to treatment arm will be determined by a computer-generated randomization list in permuted blocks of 4 to maintain balanced assignment throughout the trial. Participants must: (1) be age 18 or older, (2) have an established chronic pain disorder of at least 6 months, and (3) be receiving chronic daily oral opioid treatment. Exclusion criteria are: (1) not speaking English, (2) significant cognitive impairment that would hinder participation.

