### **Procedures**

Recruitment and Consent. Prior work in this field has demonstrated that enrollment in trials of opioid tapering can be challenging due to low rates of referral by providers and high patient refusal rates [17, 35]. We will take 2 approaches to patient recruitment. The first approach will be to invite providers who treat patients with chronic opioid therapy to refer patients to the study. This is our preferred method as it will engage the patients' current providers with whom collaboration will be crucial. We will also directly outreach to patients. The Cerner electronic medical record (EMR) can be queried by Indiana University Health (IUH) information technologist to generate a list of patients on chronic opioid therapy within the IUH System. Eligible patients will be sent a study invitation letter or text providing information unless their primary care provider disapproves. Patients interested in participating will be scheduled for a baseline study consent session. In light of ongoing fluctuations in coronavirus activity, all study activities are designed to take place virtually either over telephone or video conferencing software. Patients will be provided a copy of the study information sheet (either through U.S. post, e-mail, or access to a digital download) so they can read along during their consent session. All subjects will provide verbal informed consent and HIPAA authorization. Documentation of the informed consent process and HIPAA authorization process will be documented via the consent log in the study binder. We believe the activities in this trial satisfy the requirements outlined in 45 CFR 46.116 Part F.3 for a general waiver of written consent:

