- (1) The research involves no more than minimal risk to subjects.** All subjects eligible for the trial are on chronic opioid therapy, which puts them at risk for developing dependence, accidental overdose, and forced tapering or opioid therapy discontinuation by providers increasingly under pressure to reduce or discontinue opioid prescribing. Our intervention provides evidence-based, non-pharmacologic pain treatment that may improve pain outcomes and allow patients to decrease the doses of opioid medications they take, which would decrease their risk of the above opioid therapy-related adverse outcomes. If patients are interested in lowering their opioid dose, our program of weekly check-ins will provide a greater level of care than usual care. Patients in the usual care group are at no greater risk for adverse clinical outcomes than if they were not enrolled in the trial. The maintenance of research records and audio recordings from intervention sessions is associated with the minimal risk of potential loss of confidentiality, which is mitigated by records being maintained in a secure research environment on enterprise Microsoft Storage or REDCap databases.
- (2) The research could not practicably be carried out without the waiver.** Written informed consent will be obtained whenever a participant is able to access and utilize the electronic consent system. However, for patients without this capability, verbal consent will be obtained instead. This is preferable to the alternative approaches of either having participants return consent forms by mail or requiring participants to present to the clinic to sign consent forms. Our experience with attempting to recruit this population has demonstrated that mailing forms results in excessive delays, confusion, and frustration on the part of participants. In-person visits would result in unnecessary burdens (related to travel and parking) and potential coronavirus exposure.

**(3) The research could not practicably be carried out without identifiable data.** This is a randomized clinical trial that requires following participants over time, as well as accessing medical records to verify medication prescription information and communicate with their providers. Identifying, outreach, and following patients longitudinally cannot be accomplished without utilizing identifiable data.

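### Entry allows patients whose opioid dose is already being tapered, and prior dose trend is neither recorded nor analysed: no expected bias between arms, but a blurred 30% criterion and lost precision

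*Combined protocol and SAP*

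**What the plan says.** Study Design (section D, Approach) sets three inclusion criteria. The six-month minimum belongs to the pain disorder. The opioid criterion is only "3) be receiving chronic daily oral opioid treatment". The exclusions are complete in one sentence: "Exclusion criteria are: (1) not speaking English, (2) significant cognitive impairment that would hinder participation". Neither concerns dose.

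Allocation is 1:1, 20 per arm, from a "computer-generated randomization list in permuted blocks of 4 to maintain balanced assignment throughout the trial". No stratification factor is stated.

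Under Recruitment and Consent, "The first approach will be to invite providers who treat patients with chronic opioid therapy to refer patients to the study". This is the preferred route, and the reason given is engagement of the current provider. Direct outreach from an electronic record query is the second route. The waiver justification, item (1), lists among the risks these patients face "forced tapering or opioid therapy discontinuation by providers increasingly under pressure to reduce or discontinue opioid prescribing".

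The Outcome measures paragraph makes reduction in MEDD the primary outcome, and Table 3 schedules it at months 0 and 3. Usual-care patients stay with their own physician, with no restriction on tapering. The moderators in the Data Analysis Plan include neither prior dose trend nor prior taper. The hypothesis under the Primary Aim is that "Collaborative Care will be effective (30% reduction in mean morphine equivalent dose/day [MMED"; it names no comparator.

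**The concern.** The endpoint is a change in dose, so a dose already moving at entry acts directly on it. A patient whose physician ordered a taper shortly before consent meets every criterion, can be allocated to either arm, and cannot be told apart from a stable patient by any scheduled measure.

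Two readings of the result are affected. If the 30% criterion is judged on the intervention arm alone, reductions that would have happened anyway help to meet it. If the arms are compared, such patients add variance, and they may also dilute the difference if the programme offers them little beyond the taper they already have.

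The Data Analysis Plan intends to use whatever effect is found to size a definitive trial. Without the dose history, the team could not tell a weak intervention from a sample in which part was already tapering.

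**Working it through.** **Inputs from the Data Analysis Plan:** difference 30 mg, example 70 to 40 mg, SD 30 mg, alpha 0.05 (taken as two-sided), 20 per arm with 20% attrition, so 16 completers per arm.

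**Step 1: the plan's own figure.** Power ≈ Φ(Δ / (SD·√(2/n)) − 1.96). With Δ = 30, SD = 30, n = 16: 30 / (30 × 0.3536) = 2.828; 2.828 − 1.96 = 0.868; power 80.7% (78.1% with the noncentral t). The stated 80% is reproduced.

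**Step 2: the 30% criterion within one arm.** Assume a share f falls 30 mg on its own and the programme does nothing. The mean reduction from 70 mg is 30f / 70:

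- f = 10%: 3 / 70 = 4.3%
- f = 20%: 6 / 70 = 8.6%
- f = 30%: 9 / 70 = 12.9%

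The criterion itself is 0.30 × 70 = 21 mg. With no programme effect, it would take 21 / 30 = 70% of patients falling 30 mg, or 21 / 70 = 30% stopping entirely.

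**Step 3: between arms, two cases.** Assume that a share f of each arm falls 30 mg regardless, that other usual-care patients do not change, and that the SD of 30 applies within each subgroup.

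- *Effects add:* everyone in the intervention arm gains a further 30 mg. The difference stays at 30 mg and SD = √(900 + f(1−f)·900).
- *No extra gain:* tapering patients get nothing more from the programme. The difference is (1−f) × 30. The variance is 900 in the intervention arm and 900 + f(1−f)·900 in usual care; the SD used is the root of their average.

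| f | Add: SD | Add: power | No gain: difference | No gain: SD | No gain: power | No gain: completers per arm for 80% |
|---|---|---|---|---|---|---|
| 0 | 30.0 | 80.7% | 30 mg | 30.0 | 80.7% | 16 |
| 10% | 31.3 | 77.3% | 27 mg | 30.7 | 70.2% | 21 |
| 20% | 32.3 | 74.7% | 24 mg | 31.2 | 58.6% | 27 |
| 30% | 33.0 | 73.0% | 21 mg | 31.5 | 47.0% | 36 |

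**Step 4: chance imbalance.** With 16 per arm and simple binomial sampling, the difference in tapering share has SD √(2f(1−f)/16), which is 0.106, 0.141 and 0.162 at f = 10, 20 and 30%. Multiplied by 30 mg, the error in the contrast has SD 3.2, 4.2 and 4.9 mg, in either direction. The chance that the arms differ by three or more tapering patients is 13%, 27% and 33%. This is the same variance that raises the SD in the additive case, not a further loss.

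**Step 5: what recording status recovers.** If effects add and taper status is measured well, adjusting for it removes the f(1−f)·900 term. The SD returns from 33.0 to 30 at f = 30%, and power to about 80.7%, less one degree of freedom. In the no-extra-gain case, adjustment does not restore the difference; results by status would only show where it arises. At f = 30%, that is about 16 × 0.70 = 11 stable and 16 × 0.30 = 5 tapering completers per arm, enough for description only.

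**The case against.** A reader might infer that reductions begun before enrolment are credited to the intervention in the trial's main comparison. They are not. "Patients will be randomized to receive either the treatment intervention (n = 20) or usual care (n = 20", and the Data Analysis Plan frames the effect as a greater reduction than in usual care. Existing tapers fall on both arms alike in expectation. Only the 30% hypothesis, read without its comparator, is exposed, and Step 2 shows that pre-existing tapers would rarely meet it unaided.

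A reader might also infer that the contrast must shrink. That requires tapering patients to gain nothing from the programme. The Theory of the Intervention section argues that weaning fails for want of structure and support, which the programme supplies, so additive benefit is at least as consistent with the protocol.

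Nor do the documents say that falling doses are the natural course for these patients. The Specific Aims describe prescribing in the population, and the waiver text names forced tapering as a risk. Elsewhere the protocol says that reducing opioids in primary care is hard. That providers will refer patients they are already tapering is a plausible inference and is nowhere stated; the protocol expects few referrals and adds record-based outreach.

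Finally, this is a pilot with no formal power claim, and a stricter entry rule has a cost when recruitment is expected to be difficult.

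All of this stands, and it removes any claim of bias between arms. It does not answer the remaining point: the dose history is needed to interpret the result and is not collected.

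**Conclusion.** The point holds as one of interpretation and precision. Patients already tapering can enter and cannot be identified, in a trial whose primary outcome is dose reduction. Within the intervention arm, an assumed 10-30% of such patients supplies a 4.3-12.9% mean reduction with no programme effect. Between arms there is no bias in expectation; power falls from 80.7% to 73-77% if effects add, or to 47-70% if tapering patients gain nothing extra.

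These figures rest on assumptions the documents neither give nor rule out: the share already tapering, a 30 mg fall in those patients, and an SD of 30 that does not already include such a mix. The plan also states its 30 mg difference for the whole intervention group, so treating it as the effect in patients not already tapering is a further assumption of the no-extra-gain case. The true share may be small.

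**What to change.** 1. For every participant, abstract the prescribed MEDD over a fixed period before baseline (for example 8-12 weeks) and whether a taper was ordered or under way at entry. The waiver justification, item (3), already provides access to medical records to check prescriptions.
2. In the Data Analysis Plan, pre-specify the between-arm MEDD comparison adjusted for baseline MEDD and for the pre-baseline trend or taper status (one of the two, to spare degrees of freedom). Describe results by taper status at entry, without subgroup tests.
3. In the Primary Aim hypothesis, state that the 30% reduction is read against usual care, and report the mean reduction in both arms side by side.

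The cost is one extra abstracted item per patient and one extra covariate in a sample of about 32 completers; no recruitment is lost. Whether to restrict eligibility, and over what window, is a trade-off against recruitment that the investigators should decide.

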### **Theory of the Intervention and Conceptual Model**

The intervention is based on the observation that patients often have unchanged or improved pain when tapered from chronic opioids with a structured weaning protocol and adequate support. However, successful weaning in current practice is hindered by a lack of provider training and comfort in tapering and insufficient patient support. By providing symptom monitoring and management along with simple interventions to help patients increase their self-efficacy, we believe that patients can successfully wean from opioids. We postulate that factors such as depression, personality, catastrophizing, and severity of opioid difficulties may moderate this outcome, and will be measuring these at baseline and at 12 weeks.

### **Procedures**

Recruitment and Consent. Prior work in this field has demonstrated that enrollment in trials of opioid tapering can be challenging due to low rates of referral by providers and high patient refusal rates [17, 35]. We will take 2 approaches to patient recruitment. The first approach will be to invite providers who treat patients with chronic opioid therapy to refer patients to the study. This is our preferred method as it will engage the patients' current providers with whom collaboration will be crucial. We will also directly outreach to patients. The Cerner electronic medical record (EMR) can be queried by Indiana University Health (IUH) information technologist to generate a list of patients on chronic opioid therapy within the IUH System. Eligible patients will be sent a study invitation letter or text providing information unless their primary care provider disapproves. Patients interested in participating will be scheduled for a baseline study consent session. In light of ongoing fluctuations in coronavirus activity, all study activities are designed to take place virtually either over telephone or video conferencing software. Patients will be provided a copy of the study information sheet (either through U.S. post, e-mail, or access to a digital download) so they can read along during their consent session. All subjects will provide verbal informed consent and HIPAA authorization. Documentation of the informed consent process and HIPAA authorization process will be documented via the consent log in the study binder. We believe the activities in this trial satisfy the requirements outlined in 45 CFR 46.116 Part F.3 for a general waiver of written consent:

- (1) The research involves no more than minimal risk to subjects.** All subjects eligible for the trial are on chronic opioid therapy, which puts them at risk for developing dependence, accidental overdose, and forced tapering or opioid therapy discontinuation by providers increasingly under pressure to reduce or discontinue opioid prescribing. Our intervention provides evidence-based, non-pharmacologic pain treatment that may improve pain outcomes and allow patients to decrease the doses of opioid medications they take, which would decrease their risk of the above opioid therapy-related adverse outcomes. If patients are interested in lowering their opioid dose, our program of weekly check-ins will provide a greater level of care than usual care. Patients in the usual care group are at no greater risk for adverse clinical outcomes than if they were not enrolled in the trial. The maintenance of research records and audio recordings from intervention sessions is associated with the minimal risk of potential loss of confidentiality, which is mitigated by records being maintained in a secure research environment on enterprise Microsoft Storage or REDCap databases.
- (2) The research could not practicably be carried out without the waiver.** Written informed consent will be obtained whenever a participant is able to access and utilize the electronic consent system. However, for patients without this capability, verbal consent will be obtained instead. This is preferable to the alternative approaches of either having participants return consent forms by mail or requiring participants to present to the clinic to sign consent forms. Our experience with attempting to recruit this population has demonstrated that mailing forms results in excessive delays, confusion, and frustration on the part of participants. In-person visits would result in unnecessary burdens (related to travel and parking) and potential coronavirus exposure.

**(3) The research could not practicably be carried out without identifiable data.** This is a randomized clinical trial that requires following participants over time, as well as accessing medical records to verify medication prescription information and communicate with their providers. Identifying, outreach, and following patients longitudinally cannot be accomplished without utilizing identifiable data.

**(4) The waiver will not adversely affect the rights and welfare of subjects.** Participants will continue to receive clinical services as usual whether or not they participate in this study, and the waiver of written consent will in no way affect this.

**(5) When appropriate, subjects will be provided with additional pertinent information after participation.** All participants will continue to receive additional pertinent information whether or not they complete a written informed consent electronic document.

**Baseline Data Collection and Orientation.** Enrollment and baseline data collection will occur in 75-minute sessions over telephone or teleconferencing software. This remote approach is especially important so long as social distancing precautions are in effect to mitigate the spread of the novel coronavirus. During the first 30 minutes of the enrollment session, participants will be provided a brief overview of the study by a member of the study team, followed by distribution and explanation of the informed consent document and an opportunity for participants to ask questions. In particular, they will be given information about opioid dependence, opioid use disorder, and the potential benefit of opioid dose reduction to improve pain and reduce adverse events. They will also be informed that opioid substitution therapy is a possibility if there is concern for opioid use disorder. Once informed consent is obtained, the next 45 minutes will provide time for participants to complete baseline measures, , and receive a \$40 gift card.

### Intervention

The intervention will be a 12-week supportive opioid taper utilizing a collaborative care program consisting of 2 components: a telecare intervention and a telecare-reinforced positive psychology self-management program.

#### Opioid Reduction

**Table 2. Positive Psychology Self-Management Intervention**

Week	Program
1	Noticing and capitalizing on positive events and gratitude
2	Mindfulness
3	Positive reappraisal
4	Strengths and Attainable Goals
5	Altruism
6 - 12	Practice Your Favorite(s): Pick at least one of the prior activities you liked and practice it again.

During the initial orientation, participants will be given information about opioids and the potential benefits of opioid dose reduction. If participants are interested in reducing their opioid dose, tapering approaches will be discussed. Participants will receive education on what to expect during tapering, including possible opioid withdrawal symptoms and common treatments for each symptom. A handout describing appropriate use of non-prescription remedies for common withdrawal symptoms will be provided. The standard tapering guideline is adapted from the Mayo Clinic guidelines on opioid tapering [36]. Patients will decide whether they would like to attempt opioid dose reduction based on the standard guideline or a negotiated alternative approach as empowerment and shared decision-making can improve both patient satisfaction and adherence [37]. Any potential change in the participant's opioid dose will be discussed with the patient's treating physicians (including relevant specialists such as pain medicine providers or maternal-fetal medicine providers in pregnant participants), who will prescribe the medication. During the trial, the taper schedule can be adjusted to maximize patient tolerability, so long as the patient's treating physicians agree with the adjustment. Forced tapering can lead to negative patient outcomes including worsening pain, withdrawal symptoms, functional decline, and seeking illicit opioids [38, 39].

